6.3.2 Reporting

Any unanticipated problem that occurs during the conduct of this study and that meets **at least** the first two criteria listed in 6.3.1 must be reported to the UNC IRB using the IRB's web-based reporting system.

7.0 STATISTICAL CONSIDERATIONS

7.1 Study Design/Study Endpoints

The purpose of the study is to assess the utility of combined, simultaneous positron emission tomography (PET) and magnetic resonance imaging (MRI), collectively called PET-MR, assessing response to neoadjuvant chemotherapy in breast cancer. The overall design is to image patients with PET-MR at two time points, pre-treatment and post-treatment, and to compare results from PET-MR with those from standard-of-care MRI in the prediction of residual tumor volume. Also, secondary objectives correlate both individual and combined quantitative measures from imaging with results of pathology to determine if the PET-MR scan provides information that predicts response to chemotherapy. The primary endpoint is to compare PET-MR with standard-of-care MRI as predictors of Residual Cancer Burden (RCB) score. The secondary endpoints will address the effectiveness of the

PET metric Metabolic Tumor Volume (MTV) as a predictor of RCB and the development of a prediction model for response from combined quantitative PET-MRI measures.

Patients will be identified at the Multidisciplinary Breast Tumor Board at UNC. Patients will be breast cancer patients that are to be treated with neoadjuvant chemotherapy followed by curative intent surgery, and for whom pre- and post-treatment MRI scanning is to be part of the treatment plan. Once patient identification occurs, the patient will be assessed for the study via the inclusion and exclusion criteria mentioned above. The patient will then be approached a study coordinator and the study protocol explained and all risks outlined. If the patient provides informed consent the patient will be enrolled. Demographic data such as patient age, gender, comorbidities, and previous treatments, etc. will be collected. Tumor characteristics will be collected. All data collected will be kept on a password protected, secured server, and all physical documentation will be stored in a locked cabinet. All data will be collected by the PI and co-investigators.

Patients will then be scheduled for a pre-treatment PET-MR around the same time as clinical MRI and proceed to neoadjuvant chemotherapy per the direction of the oncologist. After therapy the patient will undergo a post-treatment PET-MR around the same time as their clinical MRI, and proceed for curative intent surgery if they are still surgical candidates.

For all PET scans, patients will be instructed to fast, and blood glucose levels will be measured prior to imaging. Patients will be injected with 10 mCi 18F-FDG, and then imaged starting 60 minutes post-injection for ten minutes each at one or two bed positions focused on the primary tumor site. MRI sequences to be run will include conventional anatomic T1- and T2-weighted sequences, high-resolution T1 pre- and post-contrast DCE sequences, and the Dixon PET-MR attenuation-correction sequence.

The PET-MRs at each time point will be evaluated retrospectively by UNC radiologists as to the size of the lesion, the FDG activity as measured by tumor-maximum and tumor-mean standard uptake values (SUVs), additional PET metrics (metabolic tumor volume (MTV) and total lesion glycolysis (TLG)), the presence or absence of invasion to adjacent organs, and the presence or absence of metastatic or multifocal disease. PET images will be evaluated with aligned anatomical MRI for guidance as well as determination of the tumor margins for computation of tumor-mean SUV.

The PET/MRs will be evaluated by UNC breast radiologists and nuclear medicine specialists as to the size of the lesion, the FDG activity as measured by SUV_{max} and SUV_{mean}, the presence or absence of invasion to adjacent organs, and the presence or absence of metastatic or multifocal disease. The pathological specimens will be evaluated by a UNC pathologist specialized in breast cancer as to (1) the size of the primary tumor, (2) the proportion of invasive carcinoma within the primary tumor

bed, (3) the number of axillary lymph nodes involved, and (4) the size of the largest metastasis in an axillary lymph node. These four quantities will be used to compute the RCB score¹. Again, all data will be stored on a secured, password protected server.

¹<http://www3.mdanderson.org/app/medcalc/index.cfm?pagename=jsconvert3>

To address the primary endpoint, image metrics from the MRI component of PET-MRI and clinical MRI will be evaluated. The principal metric to be examined is the change in tumor size from pre- to post-treatment. The change in tumor size will be correlated with RCB scores reported by the pathologist.

For the secondary endpoints, quantitative imaging measures (mean SUV, maximum SUV, MTV, TLG, MRI-based tumor volume, MRI DCE imaging parameters) will be compounded for all patients. The fractional change from pre-treatment to post-treatment will be computed for all quantities.

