1.0 BACKGROUND AND RATIONALE

1.1 Study Synopsis

The purpose of the study is to assess the utility of combined, simultaneous positron emission tomography (PET) and magnetic resonance imaging (MRI), collectively called PET-MR, in assessing response to neoadjuvant chemotherapy and surgical treatment decisions for operable breast cancers. Adult patients with operable breast cancer that are being treated at UNC with neoadjuvant chemotherapy followed by potentially curative surgical resection will be identified through the Multidisciplinary Breast Tumor Board. Patients who are being treated with neoadjuvant chemotherapy followed by surgical resection and for whom pre- and post-treatment MR imaging is part of planned treatment will undergo additional pre-treatment and post-treatment PET/MR. The response to treatment will be assessed at post-treatment by evaluating change in tumor size from MRI, change in response to dynamic contrast enhanced (DCE) MRI, and 18F-fluorodeoxyglucose (18F-FDG) avidity from PET. Patients will then undergo surgery. Their pathology will be reviewed for treatment effect as assessed by residual cancer burden (RCB) score. Patients will be followed and assessed for recurrence.

This study is designed to provide preliminary information on the progression of tumor size, DCE-MRI response, and FDG avidity during and after treatment in 25 patients diagnosed with operable breast cancer. The primary objective is to evaluate the capabilities of MRI/PET in prediction of RCB score as compared to standard-of-care MRI alone. A secondary objective will be to quantify the progression of PET- and MRI-based quantitative metrics at pre-, and post-treatment time points, and correlate these quantitative measures with RCB score.

Information from this study may be used to estimate effect size for power calculation and sample size considerations for possible future studies in the use of combined PET-MR to be used in determination of which patients are candidates for breast-conserving surgery versus mastectomy. Existing studies point to the possibility of this combined imaging information enabling more patients to be candidates for breast-conserving surgery with no impact to recurrence rate.

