2.0 STUDY OBJECTIVES/AIMS AND ENDPOINTS

2.1 Primary objectives

- 2.1.1** To compare MRI-PET with standard-of-care MRI in early prediction of response to neoadjuvant chemotherapy at pre-treatment and post-treatment time points;

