7.3 Data Analysis Plans

For the primary endpoint, each subject's change in tumor size will be correlated with the primary outcome (RCB score) and correlation estimated using the Pearson product-moment correlation coefficient. Confidence intervals on the correlation coefficient will be estimated using the Fisher transformation.

For secondary endpoint 2.2.1, the change from pre- to post-treatment in metabolic tumor volume (MTV) from PET imaging will be correlated with RCB score using the Pearson product-moment correlation coefficient. Confidence intervals on the correlation coefficient will be estimated using the Fisher transformation.

For secondary endpoint 2.2.2, each subject's set of quantitative measures will be compiled and an optimal linear regression between the image metrics and the outcome measure (RCB score) will be derived. Prediction performance will be evaluated using a leave-one-out cross-validation strategy.

For correlating individual metrics with RCB scores, with $n = 25$ subjects, we will have approximately 73% power to detect a Pearson correlation of at least 0.5, assuming a two-sided Type I error rate of 0.05 and utilizing the correlation test.

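### The primary objective compares PET-MR with MRI alone, but the primary analysis contains no PET measurement and specifies no contrast

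*Combined protocol and SAP*

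**What the plan says.** Three places state the primary question. The synopsis (1.1) has "The primary objective is to evaluate the capabilities of MRI/PET in prediction of RCB score as compared to standard-of-care MRI alone". Objective 2.1.1 has "To compare MRI-PET with standard-of-care MRI in early prediction of response to neoadjuvant chemotherapy at pre-treatment and post-treatment time points". Section 7.1 has "The primary endpoint is to compare PET-MR with standard-of-care MRI as predictors of Residual Cancer Burden (RCB) score". Sections 1.1 and 7.1 both define PET-MR as PET and MRI taken together.

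Later in 7.1 the question is put into practice: "To address the primary endpoint, image metrics from the MRI component of PET-MRI and clinical MRI will be evaluated". The principal metric is the pre- to post-treatment change in tumor size. The next paragraph places the PET quantities under the secondary endpoints: "quantitative imaging measures (mean SUV, maximum SUV, MTV, TLG, MRI-based tumor volume, MRI DCE imaging parameters) will be compounded for all patients".

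Section 7.3 gives the primary method: each subject's "change in tumor size will be correlated with the primary outcome (RCB score) and correlation estimated using the Pearson product-moment correlation coefficient", with a Fisher-transformation confidence interval. Secondary endpoint 2.2.1 correlates change in MTV with RCB. For 2.2.2, "an optimal linear regression between the image metrics and the outcome measure (RCB score) will be derived", assessed by leave-one-out cross-validation. The power statement reads "we will have approximately 73% power to detect a Pearson correlation of at least 0.5", for 25 subjects at two-sided 0.05, and is expressly about individual metrics. Section 7.2 plans 33 enrolled with 25 expected to complete.

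**The concern.** A comparison of PET-MR with MRI alone has to let PET affect the answer. As specified, the primary correlations contain two kinds of variable: RCB, and tumor-size change measured on MRI from one scanner or the other. No FDG quantity enters. PET does not enter indirectly through the size measurement either, because 7.1 uses the MRI to guide the PET reading and not the reverse.

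There is a second gap. Even for the two MRI-based correlations, 7.3 does not say which scanner's size change is used, and it names no difference, paired test, incremental measure or decision rule. Separate intervals for two correlations from the same patients do not give an interval for their difference.

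Reported under the present objective, a comparison of two MRI scanners would be presented as evidence about PET-MR. The synopsis hopes to use the results to estimate an effect size for later PET-MR studies. The primary analysis supplies no PET effect size, and the secondary analyses supply none for PET beyond MRI.

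**Working it through.** **The plan's own figure.** Inputs from 7.3: n = 25, r = 0.5 against 0, two-sided alpha 0.05.

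Power = Φ(atanh(0.5) × √(25 − 3) − 1.96) = Φ(0.549 × 4.690 − 1.96) = Φ(0.617) = 0.731.

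The 73% is reproduced. It concerns one metric against zero correlation. An observed r of 0.5 would have a 95% Fisher interval of 0.13 to 0.75.

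**Which variables enter which analysis.**

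| Analysis | Imaging input | PET? | Contrast with MRI alone? |
|---|---|---|---|
| Primary | MRI size change, PET-MR scanner and clinical scanner | No | None specified |
| 2.2.1 | MTV change | Yes | None specified |
| 2.2.2 | PET and MRI metrics in one regression | Yes | None specified |

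No row isolates what PET adds to MRI.

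**What 25 patients could show about added value.** The documents give no correlation for either modality, so these are assumptions: trivariate normal data, size change correlating 0.5 with RCB (25% of variance), PET correlating rp with RCB (0.5, 0.6 or 0.7), and PET correlating 0.3, 0.5 or 0.7 with size.

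At a PET-size correlation of 0.5:

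- Partial r of PET given size = (rp − 0.25)/0.75 = 0.33, 0.47, 0.60.
- Explained variance = (0.25 + rp² − 0.5 rp)/0.75 = 33%, 41%, 52%.

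Power of the partial-correlation t test (22 df, two-sided 0.05), from 40,000 simulated trials per cell:

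| PET-size r | PET-RCB r 0.5 | 0.6 | 0.7 |
|---|---|---|---|
| 0.3 | 56% | 82% | 97% |
| 0.5 | 37% | 66% | 90% |
| 0.7 | 21% | 52% | 85% |

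Precision: an observed partial r of 0.467 has a 95% interval of tanh(atanh(0.467) ± 1.96/√21) = 0.08 to 0.73.

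**What 25 patients could show about two correlations with RCB.** For correlations r1 and r2 with RCB, and r12 between the two predictors:

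- ψ = r12(1 − r1² − r2²) − ½ r1 r2 (1 − r1² − r2² − r12²)
- c = ψ/[(1 − r1²)(1 − r2²)]
- Power = Φ(|atanh r1 − atanh r2| × √22/√(2 − 2c) − 1.96)

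Example with 0.5 versus 0.6 and r12 = 0.9: ψ = 0.351 + 0.063 = 0.414; c = 0.414/0.48 = 0.8625; power = Φ(0.144 × 4.690/0.524 − 1.96) = 25%. At r12 = 0.3 it is 8%. For 0.5 versus 0.7, power is 20%, 25%, 37%, 51% and 81% at r12 of 0.3, 0.5, 0.7, 0.8 and 0.9. Simulating Williams' t test (20,000 trials per cell) gave similar values, the largest gap being 85.5% against 81.4% in that last cell.

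**The case against.** The strongest reply is that a scan-versus-scan comparison was meant. Only the synopsis says alone; 2.1.1 and the endpoint sentence in 7.1 could describe the MRI from one scanner set beside the MRI from the other, with PET kept for the secondary objectives. The experimental breast coil (6.2.1) makes that a sensible technical aim. This reading is possible, but it conflicts with the synopsis and with the guiding hypothesis in 1.3 that PET and MRI metrics together predict response. It also leaves the contrast undefined. The coil argument is partly met elsewhere, since image quality is to be checked in five volunteers under a separate protocol, with the built-in coil as fallback.

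Three further points are fair. First, 7.1 speaks of metrics in the plural and calls size the principal one, so other MRI metrics are not excluded; PET metrics still are. Second, the secondary analyses will give MTV and MRI correlations with RCB in the same patients, so an informal comparison is possible. What is missing is any planned paired or incremental contrast. Third, this is a pilot, and a formal test at n = 25 is weak in many of the scenarios above. That argues for an interval instead of a significance test. It does not justify estimating a different quantity from the one in the objective.

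Finally, the power figures describe the proposed remedies, not the harm done by the present text. The mismatch does not depend on them.

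**Conclusion.** The concern holds, and the plan must be changed. Followed exactly, it yields a primary result that does not depend on PET and so cannot answer the objective stated in the synopsis. That conclusion comes from the text alone. The 73% power is correct for a single correlation but does not cover the comparison named as the primary endpoint.

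Under the assumed correlations, power for PET's added value ranges from 21% to 97%. Those figures rest on multivariate normality and on a size-RCB correlation held at 0.5 throughout; other values would shift them. They support presenting the result as an estimate with its interval.

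**What to change.** Choose one of two routes.

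**A. Keep the objective.** In 7.1 and 7.3, define the primary analysis, in the same patients, as prediction of RCB from clinical-MRI size change alone versus that size change plus one PET metric named in advance (fractional MTV change is one candidate). Report the partial correlation of the PET metric given MRI size with its 95% interval, and the change in leave-one-out prediction error. Present it as estimation. Move the comparison of the two scanners' MRI size measurements to a secondary technical check. This edits 2.1, 2.2 (MTV overlaps 2.2.1, and the technical check needs its own objective), 7.1, 7.3 with its power sentence, and the synopsis where it lists secondary aims. The price is one more fitted parameter and modest power.

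**B. Keep the analysis.** Reword the primary objective and endpoint to say that MRI from the PET-MR scanner is compared with clinical MRI. State in 7.3 that the two paired correlations are contrasted by their difference with a confidence interval that allows for the shared patients. Add an MRI-only comparator model to 2.2.2, so that PET's contribution is estimated somewhere. This edits the synopsis, 2.1, 2.2.2, 7.1 and 7.3.

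Neither route needs a new scan or measurement. Either is a written amendment requiring IRB approval under 8.5.

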7.2 Sample Size and Accrual

The study will enroll 33 eligible patients that are being treated at UNC Hospitals; of these, 25 are expected to complete the study based on completion rates from previous PET-MR pilot studies at UNC.

7.3 Data Analysis Plans

For the primary endpoint, each subject's change in tumor size will be correlated with the primary outcome (RCB score) and correlation estimated using the Pearson product-moment correlation coefficient. Confidence intervals on the correlation coefficient will be estimated using the Fisher transformation.

For secondary endpoint 2.2.1, the change from pre- to post-treatment in metabolic tumor volume (MTV) from PET imaging will be correlated with RCB score using the Pearson product-moment correlation coefficient. Confidence intervals on the correlation coefficient will be estimated using the Fisher transformation.

For secondary endpoint 2.2.2, each subject's set of quantitative measures will be compiled and an optimal linear regression between the image metrics and the outcome measure (RCB score) will be derived. Prediction performance will be evaluated using a leave-one-out cross-validation strategy.

For correlating individual metrics with RCB scores, with $n = 25$ subjects, we will have approximately 73% power to detect a Pearson correlation of at least 0.5, assuming a two-sided Type I error rate of 0.05 and utilizing the correlation test.

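### The primary endpoint compares PET-MR with standard-of-care MRI as predictors of RCB, but the analysis plan gives only separate correlations, with no contrast, interval or expected precision for the difference

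*Combined protocol and SAP*

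**What the plan says.** Three places make the primary question a comparison.

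- Section 1.1: "The primary objective is to evaluate the capabilities of MRI/PET in prediction of RCB score as compared to standard-of-care MRI alone".
- Section 2.1, the only primary objective: "To compare MRI-PET with standard-of-care MRI in early prediction of response to neoadjuvant chemotherapy".
- Section 7.1: "The primary endpoint is to compare PET-MR with standard-of-care MRI as predictors of Residual Cancer Burden (RCB) score".

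Section 7.1 then names the data: "To address the primary endpoint, image metrics from the MRI component of PET-MRI and clinical MRI will be evaluated". It adds: "The principal metric to be examined is the change in tumor size from pre- to post-treatment". The post-treatment visit is described as "a post-treatment PET-MR around the same time as their clinical MRI", and the pre-treatment scans are timed in the same way.

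The primary analysis in section 7.3 is that each subject's "change in tumor size will be correlated with the primary outcome (RCB score) and correlation estimated using the Pearson product-moment correlation coefficient". The only statement on uncertainty is "Confidence intervals on the correlation coefficient will be estimated using the Fisher transformation". Section 7.3 does not mention clinical MRI under the primary endpoint; that the correlation is computed once per scanner has to be inferred from section 7.1. The one operating characteristic given is about 73% power at n = 25 for a correlation of 0.5 (two-sided 0.05), and the plan labels it as applying to individual metrics.

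**The concern.** Followed exactly, the plan produces two correlations, each with its own interval, and stops there. It does not define a difference, an interval or test for one, or a criterion for calling one modality the better predictor. The secondary analyses do not fill the gap: 2.2.1 is a single correlation with metabolic tumor volume, and the cross-validated regression in 2.2.2 names no clinical-MRI comparator.

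The two correlations are not independent. They come from the same patients, share the same RCB values, and use MRI size change from scans taken close together, so the two size measures may be highly correlated. The precision of the difference depends heavily on that correlation, and separate intervals ignore it.

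The two correlations can be subtracted, but the plan gives no valid uncertainty for the result and leaves the method of comparison open until the data are seen. Section 1.1 says the results may be used to estimate effect sizes for later studies; a comparative effect size without an interval that respects the pairing is a weak basis for that. Section 1.3 says the PET-MR scans do not guide treatment, so what is at stake is the primary result and later planning, not patient care.

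There is a related mismatch. The primary metric uses only the MRI part of PET-MR, so no PET measure enters the primary comparison.

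**Working it through.** **Inputs from the documents.** Section 7.2: 33 enrolled, 25 expected to complete. Section 7.3: correlation 0.5, two-sided 0.05, power about 73%.

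**Inputs assumed, because the documents do not give them.** True correlations with RCB of 0.3, 0.5, 0.6 or 0.7; correlation between the two size measures, r12, of 0.5, 0.8, 0.9 or 0.95; normally distributed data.

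**Step 1: the plan's own figure.** Power for one correlation against zero is Φ(atanh(r)·√(n−3) − 1.96). With r = 0.5 and n = 25 this is Φ(0.549 × 4.690 − 1.96) = Φ(0.617) = 0.731. The 73% reproduces. The Fisher 95% interval around r = 0.5 is tanh(0.549 ± 1.96/4.690), or 0.13 to 0.75.

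**Step 2: an interval for the difference.** Zou's method combines the two sets of Fisher limits (l, u) using the correlation c between the two sample correlations:

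c = [(r12 − ½·r1·r2)(1 − r1² − r2² − r12²) + r12³] / [(1 − r1²)(1 − r2²)]

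lower limit = (r1 − r2) − √[(r1 − l1)² + (u2 − r2)² − 2c(r1 − l1)(u2 − r2)]

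The upper limit mirrors this. For r1 = r2 = 0.5 and r12 = 0.8:

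- c = [0.675 × (−0.14) + 0.512]/0.5625 = 0.742
- r − l = 0.369 and u − r = 0.247
- half-width = √(0.136 + 0.061 − 0.135) = 0.25
- with c set to 0, as if the samples were independent: √(0.136 + 0.061) = 0.44

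**Step 3: expected half-widths.** These are medians over 40,000 simulated trials per scenario. They differ slightly from Step 2, which plugs in the true values.

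| True correlations, n | r12 = 0.5 | 0.8 | 0.9 | 0.95 |
|---|---|---|---|---|
| 0.5 and 0.5, n = 25 | 0.35 | 0.24 | 0.19 | 0.16 |
| 0.7 and 0.7, n = 25 | 0.28 | 0.21 | 0.17 | 0.15 |
| 0.3 and 0.3, n = 25 | 0.37 | 0.25 | 0.19 | 0.15 |
| 0.5 and 0.5, n = 20 | 0.39 | 0.28 | 0.22 | 0.19 |
| 0.5 and 0.5, n = 33 | 0.30 | 0.20 | 0.16 | 0.13 |

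Coverage of the Zou interval at n = 25 was 94.7% to 98.2% across 20 scenarios; it is conservative when r12 is high.

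**Step 4: what the separate intervals would show.** The plan does not propose combining them. A reader who did so as if they were independent would get a half-width of 0.44 at 0.5 and 0.5, which is 1.27 to 2.80 times the Zou width, with coverage from 98.7% to nearly 100%. Reading the intervals side by side gives:

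| n = 25 | r12 = 0.5 | 0.8 | 0.9 | 0.95 |
|---|---|---|---|---|
| Fisher intervals overlap, true 0.5 and 0.7 | 98.0% | 99.8% | 100% | 100% |
| Zou interval excludes zero, true 0.5 and 0.7 | 26% | 52% | 81% | 99% |
| Zou interval excludes zero, true 0.5 and 0.6 | 9% | 14% | 21% | 30% |

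The 99% is an extreme case, since that correlation matrix is nearly singular. As a single example, observed correlations of 0.5 and 0.7 have Fisher intervals of 0.13 to 0.75 and 0.42 to 0.86, which overlap widely. At r12 = 0.9 the paired interval for the difference is 0.06 to 0.45.

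**Step 5: a check by bootstrap.** A percentile bootstrap resampling patients (1,500 trials, 1,000 resamples) gave half-widths of 0.32, 0.21, 0.15 and 0.11 at 0.5 and 0.5. Coverage was 91.6% to 95.0% over 12 scenarios. It is narrower than Zou and slightly under-covers, so precision has to be stated for the method actually named.

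**The case against.** This is a pilot that promises preliminary information, with no success criterion tied to the comparison. Nothing is lost for good: the paired sizes and RCB scores will exist, and the difference can be computed under a plan fixed before analysis. Treating the intervals as independent errs on the cautious side and does not manufacture superiority. The 73% is correctly labelled. The magnitudes rest on assumed correlations, and the experimental breast coil (or the volume coil held in reserve) makes a high between-scanner correlation uncertain. Zou's interval is also conservative at high r12: at 0.95, with both correlations 0.5, its half-width is 0.157 against about 0.11 from 1.96 times the empirical standard deviation. With 0.5 and 0.6 at that r12, a Steiger test rejects in 44% of trials against Zou's 30%. Finally, an exact interval on a two-scanner MRI contrast leaves the larger question, what PET adds, unanswered.

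Most of these facts stand, but they do not close the gap. Pilot status argues for estimation over power, and a defined estimate with a valid interval is exactly what is missing. A cautious error still hides differences that the paired data could show. The spread of the magnitudes is a reason to state precision over a range. Zou is one valid choice among several, and its conservatism should be acknowledged where r12 is high. The point about PET is right, and the plan should say so openly.

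**Conclusion.** The concern holds. The declared primary endpoint is a comparison, and no analysis in the plan answers it: there is no contrast, no interval that allows for the pairing and no expected precision. The 73% power is arithmetically right for one correlation against zero and does not bear on the comparison.

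At n = 25 the difference between the two correlations would be estimated to within roughly ±0.15 to ±0.37 by Zou's method. This range covers assumed equal correlations of 0.3, 0.5 or 0.7 and a between-metric correlation of 0.5 to 0.95, with normal data. The gap itself does not depend on these assumptions; only its numerical size does.

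This needs correcting before analysis, because it concerns the primary result. Even when corrected, the contrast that section 7.1 defines is between MRI size change on two scanners. It does not isolate the contribution of PET that section 1.1 describes.

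**What to change.** In section 7.3:

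1. Define the primary estimate as the difference between two correlations with RCB, that of size change on the MRI component of PET-MR and that of size change on clinical MRI, in patients with both sets of scans and an RCB score.
2. Give a 95% interval by one named method for dependent correlations sharing a variable, for example Zou's, with a patient-level paired bootstrap as a check. Present it as estimation in a pilot.
3. State the expected half-width for the chosen method. For Zou at n = 25 with both correlations 0.5, it is about 0.35, 0.24, 0.19 and 0.16 at between-metric correlations of 0.5, 0.8, 0.9 and 0.95; if both are 0.7, about 0.28, 0.21, 0.17 and 0.15. Label these as assumptions and note that the method is conservative at the high end.
4. State that the 73% power does not apply to this comparison.
5. State that the contrast compares MRI size change on two scanners and does not by itself measure what PET adds to standard-of-care MRI alone.

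The cost is SAP wording and a few lines of code, with no new patients, scans or procedures. The stated precision may look less favourable than 73% power, and the caveat makes plain that the primary contrast does not isolate PET.

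### The primary question is PET-MR versus standard-of-care MRI, but no output specified in 7.3 quantifies what PET adds to MRI in predicting RCB

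*Combined protocol and SAP*

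**What the plan says.** The comparison is stated three times in the combined protocol and SAP. The synopsis (1.1) gives the primary objective as to "evaluate the capabilities of MRI/PET in prediction of RCB score as compared to standard-of-care MRI alone". Objective 2.1.1 reads "To compare MRI-PET with standard-of-care MRI in early prediction of response to neoadjuvant chemotherapy". Section 7.1 says "The primary endpoint is to compare PET-MR with standard-of-care MRI as predictors of Residual Cancer Burden (RCB) score".

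The analyses are in 7.1 and 7.3:

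- **Primary.** 7.1 takes metrics from the MRI part of the PET-MR scan and from the clinical MRI, principally the change in tumour size. In 7.3 each patient's "change in tumor size will be correlated with the primary outcome (RCB score"), by Pearson coefficient with a Fisher interval.
- **2.2.1.** The change in MTV is correlated with RCB in the same way, without adjustment for MRI.
- **2.2.2.** PET and MRI metrics are compiled and "an optimal linear regression between the image metrics and the outcome measure (RCB score) will be derived". Then "Prediction performance will be evaluated using a leave-one-out cross-validation strategy". No comparator model is named, and what makes the regression optimal is not defined.

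Section 7.1 adds that "secondary objectives correlate both individual and combined quantitative measures from imaging with results of pathology". On the use of the results, 1.1 says they "may be used to estimate effect size for power calculation and sample size considerations" in possible later PET-MR studies.

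**The concern.** A comparison of PET-MR with MRI alone asks how much better RCB is predicted when PET is added. None of the specified outputs is that quantity. The primary correlation contains no PET. The MTV correlation is marginal: if MTV falls only because the tumour shrinks, it will correlate with RCB while adding nothing to tumour size. The performance of the combined model mixes the contributions of both modalities, and nothing is fitted against which to read it.

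A team that follows the plan exactly would finish with an MRI correlation, a PET correlation and one combined performance figure, and would still have to choose a comparison after seeing the data. A later study designed around PET's added value would inherit no estimate of it.

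**Working it through.** **1. The plan's own figure.** Section 7.3 states about 73% power for a correlation of 0.5 with n = 25 and two-sided α = 0.05. By Fisher's z, power = Φ(atanh(0.5) × √22 − 1.96) = Φ(0.549 × 4.690 − 1.96) = Φ(0.616) = 73.1%. The figure reproduces. It concerns one correlation tested against zero, so it says nothing about a comparison of modalities.

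**2. Which output could carry the comparison.**

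| Analysis | Contains PET | Contains MRI | Isolates PET's gain as specified |
|---|---|---|---|
| Primary | No | Yes | No |
| 2.2.1 | Yes | No | No |
| 2.2.2 | Yes | Yes | No: one model, PET terms not planned for test or report |

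**3. Assumptions for an illustration.** The documents give no correlations between metrics and no effect size for PET, so all of these are assumed: normal data, n = 25, RCB variance 1, four PET metrics (mutual r 0.7), two MRI metrics (r 0.5), and PET-MRI r 0.4, with a range of 0.2 to 0.6.

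- Case A, PET adds nothing: coefficient 0.7 on MRI size. True R² = 0.7² = 0.49.
- Case B, PET adds: coefficient 0.4 on MRI size and 0.4 on one PET metric. True combined R² = 0.16 + 0.16 + 2 × 0.4 × 0.4 × 0.4 = 0.448. The two MRI metrics alone give 0.32.

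**4. The marginal PET correlation (the form of 2.2.1).**

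- Case A: r = 0.7 × 0.4 = 0.28. Approximate power is Φ(0.288 × 4.690 − 1.96) = 27%. Simulation of the t test gives 28% (10% to 57% over the range).
- Case B, for the metric carrying the signal: r = 0.4 + 0.4 × 0.4 = 0.56. Approximate power is Φ(0.633 × 4.690 − 1.96) = 84%. Simulation gives 86% (71% to 95%).

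**5. The combined model (the form of 2.2.2).** Least squares on six metrics, leave-one-out R² = 1 − PRESS/total sum of squares, simulated means at PET-MRI r 0.4:

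| | Case A | Case B |
|---|---|---|
| True combined R² | 0.49 | 0.45 |
| Combined, leave-one-out | 0.21 | 0.15 |
| MRI-only, leave-one-out | 0.37 | 0.17 |
| Gain, four PET metrics | −0.16 | −0.02 |
| Gain, one PET metric (in B, the one carrying the signal) | −0.03 | +0.11 |

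Over the range, the combined figure stays at 0.21 in A and runs from 0.05 to 0.24 in B. Its size does not show which case holds. With the MRI-only row beside it, the cases differ on average.

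**6. What an added analysis could deliver.** In case B, MRI size alone has R² = 0.56² = 0.314. The partial correlation of the PET metric given size is √((0.448 − 0.314)/(1 − 0.314)) = 0.44. With one covariate the Fisher standard error is 1/√(25 − 1 − 3) = 1/√21, so the 95% interval is tanh(0.472 ± 1.96/√21) = 0.04 to 0.72. The partial F test for PET over the two MRI metrics rejects in 31% of case B trials with four PET metrics. It rejects in 56% with the one that carries the signal, and in 24% with a different one.

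**The case against.** The strongest reply is that the plan already holds the ingredients. The 2.2.2 regression includes PET and MRI metrics together, so its PET coefficients are conditional on MRI. An undefined search for an optimal model might even visit MRI-only models. The size and MTV correlations will also stand side by side with intervals. This stands in part. A reader might infer that the plan yields no information at all on PET's added value, and that goes too far. What is missing is a specified, reported contrast with MRI alone.

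Other inferences also go beyond the documents or the figures:

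- *That the MTV correlation is uninformative.* At 86% against 28% it does differ between the cases. It just does not isolate added value.
- *That the combined model would perform well when PET adds nothing.* A mean leave-one-out R² of 0.21 against a true 0.49 is not good performance. The closeness of the two combined figures is also partly built in, because the true values were set close together (0.49 and 0.45).
- *That the documents make MTV depend on the MRI.* Section 7.1 ties MRI-drawn margins to mean SUV, not to MTV. The PET-MRI correlations here are assumptions.
- *That 1.1 names PET's gain as the effect later studies need.* It names no effect measure. The case for the gain rests on the stated comparison itself.

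Finally, this is a pilot, and any estimate of the gain will be imprecise. That is true, and it argues for presenting the result as estimation. It does not argue for leaving the comparison unspecified.

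**Conclusion.** The point holds in this form: the documents pose PET-MR against standard-of-care MRI as the primary question, and no output specified in 7.3 quantifies PET's gain over MRI. That conclusion rests on the text alone. The illustration depends on the assumed correlations and shows only that neither the MTV correlation nor the combined leave-one-out figure can stand in for the missing contrast. It does not predict what this trial will find. The change should be made before analysis, since a comparator chosen afterwards would be open to selection. In a 25-patient pilot this is a recommended change and does not invalidate the study.

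**What to change.** In 7.3, under the comparative objective:

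1. Report the partial correlation of MTV change with RCB given MRI tumour-size change, with the Fisher interval the plan already uses (standard error 1/√21 at n = 25).
2. Beside the 2.2.2 model, fit an MRI-only model on the same patients by the identical procedure. Use standard-of-care clinical MRI metrics where available, because that is the stated comparator. As a second version, use the same MRI metrics as the combined model. Repeat any metric selection inside each leave-one-out fold. Report both leave-one-out errors and their paired difference with an interval.
3. Fix a short metric list in advance, the same in 2.2.2 and 7.1 (mean SUV is now only in 7.1), with the DCE parameters named. Label the results as estimation.

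The cost is SAP wording and modest analysis work. No new scans or patients are needed, since pre- and post-treatment clinical MRI is already an entry requirement (1.3 and 3.1.5). The intervals will be wide, as the 0.04 to 0.72 above shows. The text should also warn that, with four PET metrics and least squares, the cross-validated gain can average slightly below zero (−0.02 in the illustration) even when PET adds, so a negative value would not show that PET is useless. A single-metric PET list avoids much of this only if the chosen metric carries the signal.
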